## 9.0 Risks to Participants

CONFIDENTIAL

**Metformin:** Metformin has been safely used since the 1920s, making it an appealing option for treatment in asymptomatic individuals. The most common side effects are gastrointestinal (GI), and typically happen in fewer than 15% of patients; GI side effects are minimized when metformin is taken at the end of a meal (rather than at the beginning or "with" a meal), and often subside after 5 days of regular use. The most common GI side effects are:

- nausea, vomiting, stomach pain;
- lose bowel movements
- diarrhea

We are not obtaining safety labs after starting the trial because we are not including patients on medications that increase risk for hypoglycemia (insulin and sulfonylureas), and the package insert recommends GFR monitoring only every 12 months, and monitoring B12 levels every 2-3 years in patients at risk for B12 deficiency, as participants will not be taking study drug for more than 14 days.

**Fluvoxamine:** Fluvoxamine has been safely used since the 1980s. The most common side effects are central nervous system and gastro-intestinal. About 10 to 30% of patients may experience headaches or insomnia, particularly at higher doses. About 10 to 40% or patients may experience nausea or diarrhea, particularly at higher doses. The dose used in this trial is lower than the dose typically used in clinical care with fluvoxamine.

**Ivermectin:** Ivermectin has been safely used since the 1980's. Use during infection with onchocerciasis is associated with more side effects, so persons with concomitant infection are excluded. In the absence of onchocerciasis, about 4% of persons will have tachycardia; 2% will have diarrhea/nausea; and 3% will have dizziness. About 2% to 3% of persons will also have laboratory changes (changes in CBC or transaminase levels).

See Metformin, Fluvoxamine, and Ivermectin Packet Inserts for additional drug information and risks.

9.1 Mitigation of Risk:

Metformin:

- Elevated levels of NDMA have not been found in metformin IR, immediate release. We will only use immediate release metformin, not extended release.
- In order to reduce the risk of lactic acidosis, we are excluding patients with advanced heart failure, liver failure, or renal failure, or known alcohol use disorder
- We are requiring a baseline GFR in persons > age 75, or with history of heart, liver, or renal failure, within 2 weeks before enrolling to ensure those high risk patients have a GFR > 45.

Fluvoxamine:

- We are using a low dose of fluvoxamine with only 1 dose on the first day to mitigate side effects from BID dosing on the first day.
- Ivermectin:
- While the range of acceptable and safe per kilo doses of ivermectin is large, we are using weight-based dosing.

All arms:

- We will use careful screening of exclusion criteria so that participants are excluded from arms that may include a contraindication or medication interaction.
- We are recommending that study drug be taken at the end of a small meal, and that patients abstain from alcohol use during the study period.
- We are creating an upper age limit in order to reduce the likelihood of a patient experiencing reduced GFR during the study period.
- Patients will be advised to let their providers know that they are in a research study that involves metformin, ivermectin, or fluvoxamine, and thus that they should discontinue the study medication at the time of hospitalization or before a CT scan with contrast.
- Every effort will be made to enter a Research Note into the electronic health record stating that the patient is in a double-blinded randomized trial of metformin, fluvoxamine, ivermectin, and placebo with the study number and contact information for participants who are enrolled from participating health systems.
- 9.2 Reproduction Risks:

While fluvoxamine and ivermectin may be used in pregnancy and have no known teratogenic effects, they have not been assessed in prospective randomized trials in pregnancy as often as metformin has. Thus, we will close the randomization arms that include ivermectin or fluvoxamine to pregnant women. We will have a separate group of blinded study packs for pregnant and lactating women, so that study staff will know that pregnant and breastfeeding participants are getting only either metformin or placebo, but will remain blinded to whether they are receiving metformin or placebo. Additionally, because pregnant and lactating women will be considered their own sub-study in this trial, and an important sub-study, we will enroll pregnant/lactating women down to age 18 years old. Thus, pregnant women may be analyzed as a separate substudy.

Metformin has not been found to have teratogenic effects and is commonly used in pregnancy, so we do not have a justification to exclude pregnant women. Pregnant women will be advised to inform their care providers that they are in this study. As with all participants, study procedures may be done completely virtually. If a participant prefers in-person lab draws or other procedures, every possible effort will be made to follow current standards of protecting the subject and study staff against transmission of the virus.

# 10.0 Outcomes that are specific to pregnancy, https://www.cdc.gov/reproductivehealth/maternalinfanthealth/smm/severe- morbidity-ICD.htm, will also be analyzed (they would all be captured as a hospitalization or ED visit, the primary outcomes for the main study). Potential Benefits of Treatment Arms

- 10.1 COVID-related potential benefits of Metformin:
  - 10.1.1 Observational data show associations of reduced mortality from COVID-19 in patients using metformin. There is un-published observational data showing decreased likelihood of being hospitalized for patients on home metformin. Metformin has been

CONFIDENTIAL

associated with improved outcomes in other viruses (Influenza and Zika, another RNA virus).

- 10.2 COVID-related potential benefits of Fluvoxamine:
  - 10.2.1 Fluvoxamine has been shown in a phase 2 trial and prospective cohort, as well as in vitro-studies and computer modeling, to decrease severity of COVID-19 disease.
- 10.3 Covid-related potential benefits of Fluvoxamine:
  - 10.3.1 A recent trial assessing a multi-therapy including 12mg one-time dose of ivermectin found a 75% reduction in hospitalizations. Another small double-blinded RCT showed significant increased chance of viral clearance after a 5-day course of ivermectin.

10.4 Other possible benefits:

Metformin has been associated with reduced incidence of blood clots, improved outcomes in some cancer, improved cholesterol, and improved insulin resistance, in patients with and without diabetes.

Metformin is commonly used as a chronic medication for type 2 diabetes, pre-diabetes, and often off-label use for weight management, poly-cystic ovarian syndrome, and preventing anti-psychotic related weight gain.

Additionally, 34.5% of adults in the US have prediabetes, and 90% of them have never been told about this diagnosis. Metformin is indicated for many persons with prediabetes, however only about 1% of persons with prediabetes have been prescribed metformin.

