## 3.0 Study Endpoints

3.1 Primary Endpoint:

1) Clinical progression, defined as: Emergency department visit for any COVID-19 related symptom (including hospitalization or death) or decrease in O2 saturation ( $\leq 93\%^{*59}$  on room air, or need for supplemental oxygen to maintain an O2 saturation >93%) by 14 days.

\*COVID-19-related symptoms as defined by the CDC\*, or attributed to COVID by treating team. \*https://www.cdc.gov/coronavirus/2019-ncov/symptoms-testing/symptoms.html. Currently those symptoms include: Fever or chills, cough, shortness of breath or difficulty breathing, fatigue, muscle or body aches, headache, new loss of taste or smell, sore throat, congestion or running nose, nausea or vomiting, or diarrhea.

Secondary Endpoints:

- Clinical deterioration on a Likert-type scale: (0) No symptoms (1) moderate severity of illness as defined by O2 saturation ≤93% but no supplemental oxygen requirement; (2) O2 saturation >93% plus supplemental oxygen requirement; (3) ED visit for any COVID symptoms (4) hospitalization for any COVID symptom; (5) the above, plus ventilator support requirement; (6) the above, plus ventilator support for at least 3 days; (7) death; and by number of days requiring supplemental oxygen; hospitalization; ventilator support), by Day 28. Hospitalized patients may be followed for maximal outcome.
- Time to meaningful recovery (symptoms or severity improved by one category and sustained for at least 36 hours)
- Maximum symptom severity experienced by Days 14, 28 (Appendix B)
- Incidence of all-cause study medicine discontinuation (Day 14).
- Portion of participants with Post-Acute Sequelae of SARS-CoV-2 Infection (PASC)
- a. PASC assessment monthly after enrollment for 6 months to 12 months with the "Questionnaire to characterize long COVID." (Appendix G).
- •

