## Day 28 Contact:

- Symptom log (adapted from FDA suggestions, Appendix B)
- Assess clinical progression (Query for hospitalization or ER visit or SAEs that occurred between Day 14 and Day 28)
- Assess other medicines used during study period

A vital status search will be conducted on all randomized patients.

Days are +/- 3 days, for the first 14 days every attempt will be made to capture data +/- 1 day.

Patients will be advised to seek medical care for symptoms in the same way that they would if they were not in the study.

Participants will be reimbursed for their time via a trackable means (i.e. Clin card or Visa card), after completion of these study activities: enrollment; Day 1 labs; Day 5 labs; Day 10 labs; Day 14 log returned; and Day 28 follow-up.

Monthly Contact: Patients will be assessed approximately once/month for 9 months after the completion of their Day 28 contact to assess for ongoing symptoms suggestive of post-acute sequelae of COVID-19. Patients will receive reimbursement for each of these monthly follow-ups completed.

5.6 Study Duration:

14 days of treatment with follow-up, and a follow-up survey at 28 days then monthly for 9 months.

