## 6.0 Study Population

6.1 Study Population:

Adults age 30-85 years with no prior history of SARS-CoV-2 infection and with BMI in overweight or obesity category. We will not exclude patients who have diabetes, but we will exclude patients on insulin or a sulfonylurea. Symptoms are not a requirement to enroll in the because of their subjective nature and because of wanting to start patients on study drug early in the disease course.

6.2 Inclusion and Exclusion Criteria:

Inclusion criteria	Exclusion criteria
- Positive laboratory test for active SARS-CoV-2	- Hospitalized, for COVID-19 or other reasons.
viral infection based on local laboratory standard	- Symptom onset greater than 7 days before
(i.e. +PCR) within 3 days of randomization.	randomization (symptoms not required for inclusion).
- no known history of confirmed SARS-CoV-2	- immune compromised state (solid organ transplant,
infection	bone marrow transplant, AIDS, on chronic high dose
- Age $\geq$ 30 years and $<$ 85 years	steroids)
- BMI $\geq 25$ kg/m  by self-report height/weight or	- Hepatic impairment (Child-Pugh B and C) or
$>= 23 \text{kg/m}^2$ in patients who self-identify in	that in the opinion of the investigator, would affect safety
Asian or Latinx background. 	- Inability to obtain informed consent
- Has an address and electronic device for	- Enrollment in another blinded RCT for COVID-19
communication	- Already received an effective (FDA approved/EUA*)
- GFR>45ml/min within 2 weeks for patients	therapy for COVID-19 (currently monoclonal antibody
>75 years old, or with history of heart, kidney, or	treatment)
liver failure.	- Alcohol use disorder

- Other unstable medical condition or combination of home medications that in the view of the PI make it unsafe for the individual to participate

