13.2 Serious Adverse Event (SAE)

Serious adverse events will be collected from enrollment through day 14 and 28. Investigators will determine if the event is serious or related to the study drug.

An SAE is any AE that is:

- Fatal,
- life-threatening,
- requires or prolongs a hospital stay,
- results in persistent or significant disability or incapacity,
- a congenital anomaly or birth defect, or
- an important medical event\*.

\*Important medical events are those that may not be immediately life threatening, but are clearly of major clinical significance. They may jeopardize the subject, and may require intervention to prevent 1 of the other serious outcomes noted above. For example, drug overdose or abuse, a seizure that did not result in in-patient hospitalization, or intensive treatment of bronchospasm in an emergency department would typically be considered serious.

SAEs must be entered into the study database within 24 hours of investigator awareness of the event.

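### The pregnancy-specific outcomes are not all captured by the main primary endpoint, and after Day 28 no collection is scheduled for them

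*Protocol*

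**What the plan says.** Section 9.2 makes pregnant and lactating women their own sub-study, randomized only between metformin and placebo. The prespecified analyses in section 12.3 list pregnant women as a subgroup. The last sentence of 9.2, which has run into the heading of section 10.0, adds that outcomes on a linked severe-morbidity list will be analysed. On how they are obtained it says that "they would all be captured as a hospitalization or ED visit, the primary outcomes for the main study".

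Section 3.1 defines the primary endpoint as "Emergency department visit for any COVID-19 related symptom (including hospitalization or death) or decrease in O2 saturation", read at 14 days. A symptom counts if it is on the CDC list or if the treating team attributes it to COVID-19. Section 5.5 repeats the COVID-19 restriction.

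On safety, section 13.2 states: "Serious adverse events will be collected from enrollment through day 14 and 28". Its list of serious events includes "a congenital anomaly or birth defect". The schedule of assessments has its last AE/SAE and clinical-progression entries at Day 28, with only the long-COVID assessment after that. The monthly contacts run for 9 months after Day 28 and have one stated purpose: "to assess for ongoing symptoms suggestive of post-acute sequelae of COVID-19".

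On age, section 6.1 describes the population as "Adults age 30-85 years with no prior history of SARS-CoV-2 infection" and the criteria table in 6.2 also sets a minimum of 30. Section 9.2 says "we will enroll pregnant/lactating women down to age 18 years old".

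**The concern.** The sentence in 9.2 is the only place where the protocol says how pregnancy-specific outcomes will be obtained. It treats any hospitalization or ED visit as the main study's primary outcome, which does not match the endpoint definition. An analyst who took it at face value would look for these events among the primary events and miss those unrelated to COVID-19.

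The time windows add a second gap. Many women enrolled while pregnant would still be pregnant at Day 28, and nothing scheduled after that asks about admissions, SAEs or the pregnancy. A low count of maternal events could then reflect the length of follow-up, yet be read as reassurance about metformin in pregnancy. The SAE category for congenital anomaly would mostly have no window in which it could be recorded.

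The age conflict affects who enters the same sub-study. A site that applies the 6.2 table literally has no basis for enrolling women aged 18 to 29.

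**Working it through.** The protocol gives no figure on this point to reproduce. The check compares definitions and windows, then shows how far the Day 28 limit could matter.

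**1. Type of event.**

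| | Pregnancy sentence (9.2/10.0) | Primary endpoint (3.1, 5.5) |
|---|---|---|
| Event | Hospitalization or ED visit, no cause restriction | ED visit for a COVID-19-related symptom, including hospitalization or death, or low oxygen saturation |
| Window | None stated | 14 days |

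An admission for a pregnancy complication that involves no listed symptom and is not attributed to COVID-19 fits the left column and not the right, even on Day 1. Equating the two is an error whatever the length of follow-up.

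**2. What is recorded, and until when.**

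- To Day 28: the Day 10 and Day 28 contacts ask about hospitalization, ER visits and SAEs without a cause restriction (5.5.2). Section 13.1 asks about hospitalization at every study visit. Any AE requiring a hospital stay is an SAE (13.2).
- After Day 28: only the monthly long-COVID contacts. Section 13.7 extends follow-up only for SAEs that are already open. Section 5.5 provides for an EHR search of outcomes in all enrolled patients, listed with the 14- and 28-day outcomes. No text extends it to later pregnancy events.

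**3. Share of pregnancies ending within the window.** Gestational age at entry is neither restricted nor stated, so this is an assumption shown as a range. Assume entry is uniform from week a to week 40 and delivery is at 40 weeks. Then the share ending within w days = min(1, w / (7 × (40 − a))).

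| Earliest week at entry, a | By Day 14 | By Day 28 |
|---|---|---|
| 0 | 14/280 = 5% | 28/280 = 10% |
| 13 | 14/189 = 7% | 28/189 = 15% |
| 28 | 14/84 = 17% | 28/84 = 33% |
| 32 | 14/56 = 25% | 28/56 = 50% |
| 36 | 14/28 = 50% | 28/28 = 100% |

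So most pregnancies are still ongoing at Day 28 unless entry is concentrated after about week 32.

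**4. Reach of the contacts already planned.** Nine months after Day 28 is about 28 + 274 = 302 days, longer than a full pregnancy of 40 × 7 = 280 days. Section 3.1, however, gives the monthly assessment as running 6 to 12 months after enrollment. Six months is about 6 × 30.4 = 182 days. That reaches week 40 only for women who enter at 280 − 182 = 98 days (14 weeks) of gestation or later.

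**5. Age.** Sections 6.1 and 6.2 set the minimum at 30 with no exception. Section 9.2 sets it at 18 for pregnant or lactating women. Both cannot be applied to a woman aged 18 to 29.

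**The case against.** The strongest reply is that the sentence means only that such events, if they occur during follow-up, will appear in the data as an admission or ED visit. To Day 28 that is largely right: admissions of any cause are queried, most would qualify as SAEs, and the EHR search covers all enrolled patients. A reader might infer that these outcomes cannot be captured at all, and the documents do not support that. Some obstetric presentations would even count as primary events, because the symptom list is broad (headache, nausea, shortness of breath) and attribution by the treating team suffices.

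It is also fair to say that the protocol never promises delivery or infant outcomes. It refers to a linked morbidity list, which is not reproduced. The calculation counts pregnancies ending, not events on that list, and it does not apply to lactating participants, who may already have delivered. A reader might infer that 67% to 90% of the relevant outcomes are lost (100 − 33 and 100 − 10). That range rests on an assumed spread of gestational age and omits late entry, where the loss falls to 50% or to none.

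One could add that the monthly contacts are study visits, so the section 13.1 question on hospitalization applies. The protocol does not say so, and its schedule lists no AE/SAE assessment after Day 28.

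Two things survive. The claim that all these outcomes fall within the main primary outcomes contradicts section 3.1. And no collection of admissions, SAEs or pregnancy outcomes is scheduled after Day 28. On age, section 9.2 does state its exception expressly, so sites may know of it, but the criteria table they screen from does not carry it.

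**Conclusion.** The point holds in this limited form. The capture statement is wrong in event type and window: the primary endpoint is COVID-19-specific and read at 14 days, and collection of other serious events ends at Day 28. This follows from the text alone and needs no assumption.

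The size of the later gap is not known. Under the uniform-entry assumption, between 10% (entry from week 0) and 100% (entry from week 36) of pregnancies end by Day 28. The main efficacy comparisons are unaffected. What changes is what the pregnancy sub-study can conclude: as written, it can describe events to Day 28 and cannot speak to later maternal events or to the listed congenital-anomaly category.

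The age conflict between 6.1/6.2 and 9.2 is separate and plain on the text.

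**What to change.** 1. In the pregnancy sentence, delete the word claiming completeness and the description of these events as the main study's primary outcomes. Analyse the listed pregnancy outcomes as a separate outcome, drawn from all-cause hospitalization, ED and SAE data.
2. For participants pregnant at entry, choose one of two options and state it:
   - add a pregnancy-outcome and SAE query to the monthly contacts and EHR review already planned, through the end of pregnancy, and align 13.2 and the schedule of assessments; or
   - state that the analysis covers events to Day 28 only and cannot address delivery or infant outcomes.
3. If the first option is chosen, reconcile the 9 months in sections 5.5.2 and 5.6 with the 6 to 12 months in 3.1, because the shorter reading does not span a pregnancy entered before about week 14.
4. Reconcile the age limits in 6.1 and 6.2 with 9.2.

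The cost is protocol wording and, under the first option, a few questions at contacts that are already scheduled and reimbursed. SAE reporting runs somewhat longer for this subgroup. Section 15.2 describes access to participants' own records, so infant status would come from the mother's report unless access to infant records is arranged. No additional visits or participants are needed.

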## 11.0 Data and Specimen Banking

11.1 Storage and Access:

Study data will be recorded and retained within a University of Minnesota REDCap database with study personnel being granted access to the database based on need as listed in the Delegation of Authority log.

The electronic consent (eConsent) forms will be maintained in a University of Minnesota REDCap database.

Biologic specimens intended for research beyond the study outcomes, provided by patients, may be processed by the University of Minnesota BSL2+ laboratory and frozen at -80 C. Samples will be deidentified and labeled only with a patient's study ID number.

Only authorized study team members will have access to data/specimens, expect as detailed in section 11.2.

11.2 Release/Sharing:

Data will be shared among members of the study team with appropriate access based on study role, training, and delegation of authority. Data will be made available to assigned study monitors, the data safety monitoring board, the appropriate University of Minnesota oversight authorities, the Food and Drug Administration, and other state and federal regulatory authorities as required by state and federal law.

De-identified specimens and data may be shared for future research. Requests will be evaluated on a case-by-case basis. No data will be released without proof of IRB approval or determination. Agreements as required by local policies will be completed when necessary, including data use agreements and material transfer agreements.

## **12.0** Statistical Considerations

A detailed statistical analysis plan (SAP) will be included as an appendix and developed by the statisticians prior to analyzing unblinded data. The SAP may be amended as needed thereafter by the blinded statistician(s). All analyses will follow a modified intention to treat (mITT) approach, excluding participants who were screen failures or who did not ingest any study drug, unless specified otherwise.

12.1 Randomization:

Eligible and consenting participants who test positive will be enrolled and randomized evenly among the arms for which they are eligible, i.e. 1:1:1:1:1:1 for participants who are eligible for all 6 arms. Randomization will be stratified by study site from which their IP is dispensed. Stratum specific schedules will be preemptively generated using mass-weighted urn randomization with a total mass of  $\alpha = 6$ , which is a generalization of randomly permuted blocks that reduces predictability of future assignments. Patients eligible for one study drug and ineligible for another, who are still interested in the trial, may be randomized amongst the study drug arm for which they are eligible. Randomization schedules will be generated for each possible drug eligibility pattern, and assignments will be drawn sequential from each stratum specific sequence therein. Statistical analyses will be study drug specific and consist of all participants who were eligible for and randomized into the relevant arms. Direct comparisons of study drugs and evaluation of drug-drug interactions will be conducted amongst participants who were eligible for both drugs in the comparison/interaction.

12.2 Blinding:

Study drug will be prepared by an unblinded study pharmacy team. Study personnel and participants will be blinded to participant assignments and outcomes data for the duration of the study, excepting lab data as detailed below and situations that require the blind to be broken for safety reasons. These instances will be recorded and reported to the PI and DSMB. An unblinded analysis of the laboratory outcomes from the treatment cohort sub-study will be carried out by the unblinded statisticians and shared with the blinded investigators and potential sponsors of the trial.

12.3 Sample Size Assumptions:

The statistical design is for the comparison of metformin vs placebo, controlling for the effect of fluvoxamine and ivermectin.

Sample size estimates are based on a marginal test of metformin versus placebo comparison, controlling for fluvoxamine and ivermectin use, and selected to provide at least 80% power with

5% two-sided type I error rate for the target effect indicated by the event rates in the above figure and described in detail in subsection 12.3.1. The sample size estimates are also inflated by 11% and rounded to account for interim analysis plan (see subsection 13.4) and study withdrawals.

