# Factorial design maximizes the use of placebo

Each patient gets 2 types of pills		Metformin (n=563)	Placebo (n=187)	
	Fluvoxamine (n = 375)	Metformin / Fluvoxamine n =188 6% event rate if both effective	Fluvoxamine / placebo n=187 11% event rate	
	Ivermectin (n=375)	Metformin/Ivermectin n = 188 6% event rate if both effective	Ivermectin/Placebo n = 187 11% event rate	
		Metformin / placebo n = 187 11% event rate	Placebo / Placebo n=187 20% event rate	
	Total	563	561	

[figure not shown]
• If two medications are effective, we will have 80% power to detect a difference over placebo.

• If only one medication is effective, we will have 90% power to detect a difference over placebo.

• Assumes a 10% loss to follow-up rate.

These considerations result in a planned enrollment of 1,124 participants (187-188 in each arm). Because these sample size calculations are based on marginal tests, the actual power may be higher when based on the planned tests using adjusted logistic regression models adjusted for various predictive factors as described later.

VERSION 3.4

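### Section 12.3 attributes the 1,124 sample size to the metformin test, but the printed 337 per group and 80%/90% power belong to the fluvoxamine and ivermectin comparisons

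*Protocol*

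**What the plan says.** Section 12.3 (Sample Size Assumptions) opens with the purpose of the design: "The statistical design is for the comparison of metformin vs placebo, controlling for the effect of fluvoxamine and ivermectin". It then gives the basis of the calculation: "Sample size estimates are based on a marginal test of metformin versus placebo comparison, controlling for fluvoxamine and ivermectin use", "selected to provide at least 80% power with" a "5% two-sided type I error rate for the target effect indicated by the event rates in the above figure". On inflation it says: "The sample size estimates are also inflated by 11% and rounded to account for interim analysis plan" and withdrawals.

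The factorial table that follows has six arms of 187 or 188. The event rates are 20% on double placebo, 11% on any single drug and 6% on metformin plus either other drug. The notes under the table say "If two medications are effective, we will have 80% power to detect a difference over placebo", give 90% if only one drug works, and add "Assumes a 10% loss to follow-up rate". The section concludes: "These considerations result in a planned enrollment of 1,124 participants".

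Section 12.3.1 (Hypothesized Rates) gives 337 per comparison group as the number needed for 80% power at 20% v 11%, two-sided 5%. Under Prespecified analyses, the total is later raised to 1,350, and the reason given is power for fluvoxamine and, similarly, ivermectin.

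**The concern.** In the factorial table, metformin is compared over all six arms (563 v 561). Fluvoxamine and ivermectin are each compared over four arms (about 375 v 374). One pair of power figures cannot describe both sizes of comparison, and a per-group number derived for one does not carry over to the other. If the printed numbers come from the smaller comparisons, the protocol names the wrong test as the source of its sample size and never states metformin's power. Efficacy and futility are monitored separately for each drug (Section 12.4.2), so a reader needs to know which power belongs to which drug.

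**Working it through.** **Inputs.** All come from Sections 12.3 and 12.3.1: the arm event rates above, equal allocation over six arms, two-sided 5%, 10% loss. Group rates are simple averages over arms.

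**Formula.** Two proportions, pooled variance under the null, with p the mean of the two rates:

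n per group = [1.960 x sqrt(2p(1-p)) + z_power x sqrt(pC(1-pC) + pT(1-pT))]² / (pC - pT)²

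Power comes from solving the same expression for z_power.

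**1. The plan's own figures, fluvoxamine (or ivermectin) comparison**
- Control (11 + 20)/2 = 15.5%; treated (6 + 11)/2 = 8.5%; p = 12%.
- n = [1.960 x 0.4596 + 0.842 x 0.4569]² / 0.07² = 337.1 per group. Printed: 337.
- Power at 337 per group: 80.0% for 15.5% v 8.5% (metformin also works) and 89.9% for 20% v 11% (only this drug works). Printed: 80% and 90%.
- Two of the six arms make one group, so the total is 3 x 337/0.9 = 1,123 (3 x 337.1/0.9 = 1,123.7). Printed: 1,124. Using x 1.11 instead gives 1,122.

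**2. The test the text names, metformin**
- All three drugs work: control (11 + 11 + 20)/3 = 14.0%; treated (6 + 6 + 11)/3 = 7.67%.
- n for 80% power = [1.960 x 0.4395 + 0.842 x 0.4373]² / 0.0633² = 377 per group, not 337.
- At 337 per group this test would have 75% power, not 80%.
- Evaluable size at 1,124: 1,124 x 0.9/2 = 506 per group.

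| Drugs that work | Control v treated | Metformin power at 506 per group |
|---|---|---|
| All three | 14.0% v 7.67% | 90.1% |
| Metformin and one other | 17.0% v 9.33% | 95.1% |
| Metformin alone | 20% v 11% | 97.8% |

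A simulation of a stratified Mantel-Haenszel test with 10% loss gave 90.6%, 95.2% and 97.8% for these three rows. For fluvoxamine it gave 81.0% with metformin also working and 90.5% with fluvoxamine alone. Stratification therefore does not change the picture.

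**3. The 337 in Section 12.3.1**
- 20% v 11% at 80% power needs 253 per group (275 with continuity correction).
- 20% v 11% at 90% power needs 338 per group, so 337 gives 89.9%.
- The sentence therefore pairs the right number with the wrong power for that effect.

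**4. The column heading**
- The control column is headed 187, but its three arms of 187 sum to 561, which is the total printed at its foot.

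**The case against.** Four points on the other side have force.

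- **No printed power is false for metformin.** The text promises at least 80%, and metformin has 90% to 98%. The two power notes name no drug, so they can be read as floors that hold for whichever comparison is smallest. This stands. The fault lies in the stated derivation and the missing label.
- **The total alone does not settle the matter.** Metformin at 90% power with all drugs working needs 504 per group, and 2 x 504/0.9 = 1,120, which is also close to 1,124. This stands too. But that route contradicts the 337 per group, the 80% target and the assignment of 90% to a single effective drug. Only the fluvoxamine or ivermectin comparison fits all the printed figures together.
- **The current total already rests on the other two drugs.** The rise to 1,350 is justified by fluvoxamine and ivermectin power. This limits the consequence. It also shows that Section 12.3 still carries a basis that the later text does not use.
- **The error is conservative for metformin.** This is true, and neither the design nor participants are affected.

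A reader might also infer that the text calls metformin the limiting test. It names metformin as the basis but nowhere calls it limiting. Nor does it follow that 1,124 is too large by about 286 (1,124 - 838). The 838 (2 x 377/0.9) holds only if all three drugs work, and it turns a minimum of 80% into a target of exactly 80%. Finally, nothing shows that the DSMB would apply the wrong power to all three drugs: it was shown and approved the re-calculation procedure behind 1,350, and futility is supplemented by conditional power.

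**Conclusion.** The stated basis of the sample size is wrong as written. The 337 per group and the 80%/90% power come from the two-arm against two-arm comparison of fluvoxamine or ivermectin, not from the metformin test. Like for like, metformin's power at 1,124 is 8 to 10 points above the printed figures: 90% v 80% at the table's full set of rates, and 98% v 90% with one effective drug. Setting metformin's 95% (metformin and one other) against the printed 80% would give 15 points. I do not use that gap, because Section 12.3 defines its target effect by the table's rates.

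These figures assume the table's event rates, equal arms, 10% loss and a fixed-sample test without the interim boundaries. Metformin's power at 1,350 cannot be computed from the protocol, which does not print the updated placebo event rate. This is a correction to the record of a calculation. It is not a sign that the trial is too small or too large.

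**What to change.** 1. In Section 12.3, say that the size is set by the fluvoxamine and ivermectin comparisons (two arms against two; 15.5% v 8.5%; 337 evaluable per group).
2. Label the 80% and 90% notes under the table as the power for fluvoxamine and for ivermectin.
3. Give metformin's power separately: at 1,124 (about 90%, 95% and 98% for the three scenarios, fixed-sample) and at 1,350 under the updated event-rate assumptions.
4. In Section 12.3.1, correct the 337 statement: it gives 80% power for 15.5% v 8.5% and 90% for 20% v 11%. At 80% power, 20% v 11% needs about 253 per group. Items 1 and 4 must be made together, or the two sections will assign 337 to different effects.
5. Change the control column heading from 187 to 561.

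The cost is a few sentences, one column label and one recalculated power line per drug. Neither the design nor enrolment changes.
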